#### 2.4 Pragmatic Trials in Dialysis

Given the nature of hemodialysis, specifically that dialysis is conducted similarly across the country in facilities that typically vary in size from serving approximately 30 to 200 patients and that dialysis facilities, as a part of routine care, measure laboratory tests, collect demographic information and track patient outcomes, dialysis facilities are well situated for pragmatic clinical trials. Nephrology, among medical subspecialties, has the fewest randomized clinical trials (Figure 4). This is particularly notable in dialysis, where a review of the NIH eReporter on September 24, 2015 revealed only three R01 or U01 mechanism clinical trials addressing therapies in dialysis patients, all of which are designated as pilot studies. Given that care of dialysis patients comprises more than 5% of all Medicare expenditures and that mortality rates, hospitalization rates and

rehospitalization rates among dialysis patients remain very high, adequately powered randomized trials in nephrology are urgently needed to identify effective and safe treatments for this population. Similarly, a search of Clinicaltrials.gov on September 24, 2015 of active intervention trials in dialysis reveals 120 trials, almost all of which are either very small or are evaluating new pharmacologic agents for treating anemia or mineral and bone disorder, areas where there is substantial financial potential for pharmaceuticals.

The largest ongoing clinical trial in dialysis is an exception to this trend in the United States. Titled '*A Cluster-randomized, Pragmatic Trial of Hemodialysis Session Duration (TiME)*', this trial (clinicaltrials.gov: NCT02019225) is a joint undertaking by Fresenius Medical Care, DaVita, the University of Pennsylvania and the National Institutes of Health National Institute of Diabetes and Digestive and Kidney Diseases. A cluster-randomized, parallel-group pragmatic clinical trial, the

[figure not shown]

Figure 4. Randomized controlled trials published in nephrology and 12 other medical subspecialties. Nephrology is represented by the green line at the bottom of the figure.

The investigators are targeting an enrollment of more than 6000 incident hemodialysis patients through randomization at the level of the dialysis facility.

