### **3.8 Randomization:**

Facilities will be randomized 1:1 to study arms, blocked by region and facility size (small, medium, large). If possible, randomization will occur concurrently for all participating facilities and with protocols available for prescribing immediately by physicians in the facility in the medical information system. Alternatively, depending on the time needed for facilities to approve the trial, we will randomize facilities over several months. Randomization will be performed by DCI's

Information Services (IS) personnel. DCI's IS personnel have experience with randomized clinical trials (RCTs), having designed and overseen an electronic algorithm that randomized patients to treatments arms across 3 strata in a past RCT conducted within DCI. They will create the master file of the treatment assigned to each facility. During the course of the trial, although facilities and patients and providers at those facilities will know their own randomization assignment, this information will not be made widely available to other dialysis units, physicians, patients, or staff, with the exception of the Data Safety Monitoring Board.

Approximately within four weeks following randomization, either treatment to usual care will be continued or treatment to the intensive protocol will begin depending on which protocol the unit has been assigned to as well as whether the patient agreed to be in the study. This gap is to allow sufficient time for patients in facilities to receive and review the information sheets as well as allow for educational materials to be posted in dialysis facilities.

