#### **3.9.1. Sample Size Considerations:**

Given that the study, due to its pragmatic nature, will be relatively inclusive, we anticipate a death rate consistent with the general dialysis population. For incident dialysis patients in 2010, based on USRDS data, the mortality rate peaked at 440 deaths per 1,000 patient years at risk in month two then fell to 201 in month 12. Given that most patients will be prevalent patients and that most patients who are incident will receive nutritional supplements regardless of randomization assignment, we estimate a mortality rate closer to 15-17% and have considered the lower end of this range, in our power calculations to be conservative.

To determine the sample size, many assumptions are needed. Assuming a non-linear median 4 year

survival for hemodialysis patients, we used a two-sided logrank test with an overall sample size of 3351 subjects (1675 in the usual care group and 1676 in the intensive supplement group) followed for 3 years, achieving 80% power at a 2-sided 0.05 significance level to detect a hazard ratio of 0.85 when the usual care group hazard rate is considered 0.173. This power calculation assumes all subjects begin the study together (no accrual periods). The proportion dropping out of the usual care group is 0.05, and the proportion dropping out of the intensive supplement group is also 0.05. Accounting for the cluster randomized design and an intraclass coefficient of 0.01, based on blocking by facility size and region, approximately 5500 patients in 86 facilities of average size of 65 participants will be needed. This sample size is liberal, as, once a facility is randomized to a treatment arm, new patients will continue to initiate dialysis within that facility. Through study completion, patients initiating dialysis in a facility will receive that facility's treatment. Those initiating dialysis in the final nine months of the study will not be included in primary analyses as patients receive nutritional supplements during the first 90 – 120 days of maintenance hemodialysis regardless of facility randomization arm. Factoring in 2 interim analyses using an O'Brien Fleming Test to allocate the alpha over three analyses inflates the sample size by factor of 1.017. Thus, the total sample size is 5597 patients, a small increase that will readily be accounted for with inclusion of incident patients in participating facilities over the first year of the trial.

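### Section 3.9.1 inflates for clustering as if every facility had 65 participants; with facilities of unequal size, 5597 patients give somewhat less than the stated 80% power, by an amount the documents do not allow one to fix

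*Combined protocol and SAP*

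**What the plan says.** Section 3.9.1 rests on a log-rank calculation. Before any allowance for clustering, the number required is given as an "overall sample size of 3351 subjects (1675 in the usual care group and 1676 in the intensive supplement group"). Follow-up is 3 years, and the design is described as "achieving 80% power at a 2-sided 0.05 significance level to detect a hazard ratio of 0.85". The usual care hazard is 0.173. The text adds: "This power calculation assumes all subjects begin the study together (no accrual periods"). On losses it says "The proportion dropping out of the usual care group is 0.05", with the same figure for the other arm.

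With an intraclass coefficient (ICC) of 0.01, it concludes that "approximately 5500 patients in 86 facilities of average size of 65 participants will be needed". A factor of 1.017 for two interim analyses brings the total to 5597.

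The section calls this size liberal because new patients keep entering the randomized facilities. It looks to first-year incident patients to cover the interim increase, and it leaves those who start dialysis in the last nine months out of the primary analysis. It gives no number of incident patients.

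On facility size, section 3.8 says randomization is "blocked by region and facility size (small, medium, large"). Section 2.4 describes dialysis "facilities that typically vary in size from serving approximately 30 to 200 patients", and section 2.3 gives the same range for free-standing units in the United States. No section gives the size distribution of the randomized facilities or a CV.

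**The concern.** The design effect 1 + (m - 1) x ICC is exact only when every cluster has the same size m. When sizes vary around the same mean, large facilities contribute more correlated patients than small ones save, and the variance of the treatment comparison rises. Blocking by size balances the arms but does not remove this cost. A plan that expects small, medium and large facilities and inflates only for the mean therefore states more power than its inputs deliver.

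What is at stake is how a null result is read. Under section 3.13, participants would be told after a null result that mortality showed no significant effect and that returning to usual care is reasonable. The power figure behind that message should be one the design supports.

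**Working it through.** **Inputs.** From section 3.9.1: HR 0.85, two-sided alpha 0.05, power 80%, hazard 0.173 per year, 3 years, dropout 0.05 per arm, ICC 0.01, mean size 65, 86 facilities, factor 1.017. The time unit for dropout is not stated; 5% per year reproduces the plan's figure. The CV of participants per facility is not in the documents and is an assumption throughout.

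**1. Unclustered size.** Events = 4 x (1.960 + 0.8416)^2 / (ln 0.85)^2 = 1189. The 3-year event probabilities with 5% per year loss are 0.378 and 0.332, mean 0.355. 1189 / 0.3551 = 3348 (plan: 3351).

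**2. Clustering and interim inflation.** Design effect = 1 + 64 x 0.01 = 1.64. 3351 x 1.64 = 5496 (plan: about 5500). 5496 x 1.017 = 5589 (plan: 5597). 5589 / 65 = 86.0 facilities (plan: 86). The plan's figures are thus the equal-size formula.

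**3. Slack.** 5597 / 1.017 / 1.64 = 3356 effective patients against 3351 needed, or 80.1% power.

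**4. Unequal sizes.** Design effect DE = 1 + ((1 + CV^2) x 65 - 1) x 0.01. Power = Phi(2.8016 x sqrt((5597 / 1.017 / DE) / 3351) - 1.960). At CV 0.5, DE = 1 + (81.25 - 1) x 0.01 = 1.8025. The effective size is 3053, and power is Phi(0.714) = 76.2%.

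**5. Optimal facility weighting.** Relative efficiency = 1 - CV^2 x L(1 - L), with L = 0.65 / (0.65 + 0.99) = 0.396. DE is then 1.64 divided by this efficiency.

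| Assumed CV | DE, unweighted | Power at 5597 | N for 80% (with 1.017) | DE, weighted | Power at 5597 |
|---|---|---|---|---|---|
| 0 | 1.64 | 80.1% | 5589 | 1.64 | 80.1% |
| 0.3 | 1.70 | 78.7% | 5788 | 1.68 | 79.2% |
| 0.4 | 1.74 | 77.6% | 5943 | 1.71 | 78.5% |
| 0.5 | 1.80 | 76.2% | 6143 | 1.74 | 77.6% |
| 0.65 | 1.91 | 73.7% | 6525 | 1.82 | 75.7% |

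The CVs are illustrative. If the national range of 30 to 200 applied with mean 65, range/6 would give 170/6/65 = 0.44 and range/4 would give 0.65. The randomized facilities could vary less.

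**6. Could incident patients make up the loss?** Assume 65 patients per facility at the start, r incident patients per facility-year entering for 2.25 years (3 years less the excluded nine months), time 0 at day 90 (section 3.16), and the same hazards and dropout. The mean event probability of an incident patient is then 0.215.

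- Events per facility: e = 65 x 0.3551 + r x 2.25 x 0.215, with e0 = 23.1 at r = 0.
- Design effect: 1 + (1 + CV^2) x 0.64 x e / e0, so the added patients enlarge the same clusters.
- Power: Phi(0.1625 x sqrt(86e / (4 x 1.017 x DE)) - 1.960).

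At CV 0.5, r = 5 gives e = 25.5, DE = 1.88 and 78.5% power. r = 10 gives e = 27.9, DE = 1.97 and 80.4%. The intake rate is not in the documents. For scale, 65 patients at hazard 0.173 have about 11 deaths a year, so r = 10 roughly replaces deaths.

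**The case against.** The strongest reply is that section 3.9.1 already expects more patients than it counts. Its total is to be completed with incident patients from the first year, so later eligible entrants come on top. Step 6 shows that an intake close to replacement of deaths would restore 80% at CV 0.5, even with enlarged clusters and shorter follow-up. A reader might infer from the table that the trial is underpowered. The documents do not support that: the intake is not given, and at plausible values it can cover a moderate loss.

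A reader might also take 30 to 200 as the range of the trial's own facilities and conclude that power is 74% to 78%. That does not follow either. Sections 2.3 and 2.4 describe US facilities in general and count patients treated, whereas the 65 in section 3.9.1 counts participants. At CV 0.3 the loss is only about 1 point, and a weighted analysis reduces it further.

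Finally, section 3.11 reports the interim analysis as done, so the correction changes a descriptive statement and not an estimate or a test.

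All of this limits the size of the point and leaves its core. The stated calculation has no slack and no term for unequal sizes. Section 3.9.1 uses incident patients to cover the interim increase and never links them to facility-size variation. Sections 3.9 and 3.16 name no clustered analysis method, so the gain from optimal weighting cannot be presumed.

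**Conclusion.** The point holds as an error in the stated calculation. On the plan's inputs, 5597 patients in 86 facilities of differing size give less than 80% power. The direction is certain once sizes vary appreciably; the amount depends on a CV that the documents do not give. Over assumed CVs of 0.3 to 0.65 the unweighted loss runs from a little over 1 point to a little over 6, and with optimal weighting from about 1 point to a little over 4. These figures hold the total at 5597, with full 3-year follow-up as the plan assumes. Whether the completed trial falls short of 80% is not established, because incident patients beyond 5597 are uncounted. The correction is cheap and worth making.

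**What to change.** In section 3.9.1, replace the equal-size design effect with 1 + ((1 + CV^2) x m - 1) x ICC, taking m and the CV from the actual participant counts of the randomized facilities, which the provider's information system should supply. Restate the power at 5597 from that CV; do not insert a fixed range such as 74% to 78%. If a facility-weighted analysis is intended, name it and use its design effect.

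If incident patients are relied on to keep 80%, count them explicitly, with the enlarged facility sizes, the day-90 start and their shorter follow-up. State the entry cut-off used: section 3.9.1 excludes the last nine months, while section 3.13 admits patients until about four months before primary censoring.

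The cost is one recalculation and a few sentences. No added enrolment is needed. The downside is that the stated power may be a few points lower.

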### **3.10 Internal Data and Safety**

Dialysis staff at all participating facilities will have all central research staff contact information in case of questions. Periodic study updates may occur in a variety of ways, some examples may include, during study phone calls which will be open to any staff at participating facilities if they wish to participate, through newsletters from the study office to participating units, and in person during the DCI spring medical directors' meeting, which is attended by a majority of DCI facility medical directors, as well as at the annual DCI meeting, which is attended by medical directors, nurse managers, administrators, and charge and education nurses.

### **3.11 External Data and Safety Monitoring**

An external Data and Safety Monitoring Board will be appointed prior to study start, consisting of nephrologists with experience in caring for dialysis patients, and, preferably, with experience in clinical trials, as well as a statistician with clinical trial experience. The DSMB will review separation across treatment arms and adverse events (deaths and hospitalization rates) tabulated by treatment arm once during the course of the trial. These data will be extracted from DCI's MIS at

the time of analysis. There will be one planned interim analyses of death and all-cause hospitalization. The first interim analysis was conducted after approximately 18 months from the time the first facility is randomized. A second interim analysis was initially planned; however, following the DSMB's interim analysis and after reviewing the time frame for the second analysis relative to the first analysis, including that the trial would essentially be complete by the time the DSMB's analysis would occur, the DSMB supported the PI's plan to reduce the number of interim analyses to a single analysis. Under the O'Brien Fleming test, the p values that will be required to reject the null hypothesis at each interim analysis must be less than 0.0005 at the first interim analysis; 0.0142 at the second interim analysis; and 0.0456 at the final analysis. Investigators will remain blinded to these interim analyses. The DSMB will advise the Sponsor and Principal Investigator about continuation of the study after the interim analysis.

### **3.12 Data Confidentiality and Storage**

All data pertaining to treatment and follow-up of study patients, including labs drawn as a part of routine care and outcomes, will be based on the data that is generated in routine practice currently. There will be no paper data collection forms and no additional data collected outside of that routinely collected in clinical practice. All of these data exist in electronic form within the MIS and will transfer into the research database for analysis. Patient level data within the research database will be identified by study identification number. The link between the DCI medical record number and the study identification number along with the patient's treatment assignment will be maintained by DCI's Information Services. Electronic data within the MIS and the research database are secured behind DCI's firewalls. The DSMB will be provided with a de-identified dataset for interim analyses.

### **3.13 Transition at Closeout of the Study**

Enrollment is scheduled to end in January 2020. Given that all patients at DCI facilities receive oral nutritional supplements for their first 90 days, the exposure does not differentiate until after this incident period. In this context, we will end all new enrollment at the end of 2019, continuing participants within their facility-assigned study stratum for an additional six months. To avoid patient frustration with the change in management at intervention sites, we will intensify communication with additional patient facing study materials at the facilities randomized to the intensive nutritional supplement protocol. The administrative censoring date for primary analyses would be April 30, 2020, allowing for a minimum of 1 month of separation among those consented

in late 2019, with secondary analyses extending to June 30, 2020 to maximize available data. The 2 month interval between these will allow preliminary results to be shared with study participants at the time of termination of the intervention.

This will result in one of two conclusions being relayed to study participants in this cluster randomized pragmatic trial: 1) there is no significant effect on mortality with continuing nutritional supplements once albumin is sustained in a normal range and therefore it is reasonable to revert to the usual care protocol; or 2) nutritional supplements were effective but intensive supplementation must end until the OIG has revised their opinion stating that continued intensive supplement is not in violation of the Federal anti-kickback statute. Given the increase in practice models being promulgated by CMS and the Centers for Medicare and Medicaid Innovation (CMMI) and active review of anti-kickback regulation by Health and Human Services, we are hopeful that, if data are positive, we would be able to obtain a waiver to allow oral nutritional supplement administration regardless of serum albumin levels as a part of these programs with a minimal interval between study termination and wider implementation in usual clinical care.

After the six month extension, all enrolled patients will be treated per their primary nephrologist's direction; for patients receiving usual care, this will continue unless the physician elects to discontinue this prescription. For those randomized to the intensive protocol, the intensive protocol order will be discontinued and an order generated for the usual care protocol that will need to be electronically signed by the physician prior to prescription. These procedures have been reviewed with the three member DSMB, who have approved of these changes.

### **3.14 Risk/Benefit Assessment**

Hemodialysis is a catabolic procedure, associated with amino acid loss and protein-energy wasting. Mortality and morbidity are high among hemodialysis patients, many of whom face nutritional challenges due to anorexia, fatigue, intercurrent illness and demands on time. Currently, the Office of the Inspector General, in an opinion rendered to a single dialysis provider, views administration of oral nutritional supplements in the dialysis facility as permissible under federal regulations to individuals with low serum albumin; this policy motivates the usual care arm in this research protocol, and this usual care protocol is currently used throughout DCI and, with only slight differences, in many dialysis facilities operated by other providers across the United States. The broadening of supplement administration in this research trial has no known medical risks and

may have considerable benefits, reflecting many factors. Among these factors are: 1) replacement of amino acid losses that occur as a result of the dialysis session itself; 2) a drop in serum albumin, which is only measured monthly by dialysis facilities, may be a late marker of increased catabolic challenge to an individual dialysis patient; and 3) there is no threshold level shown in observational studies for albumin above which there is not a lower risk of mortality or hospitalization.

Included in this study will only be facilities who are currently utilizing the existing nutritional supplement protocol in the majority of patients, further reinforcing that there will be no change in care for those facilities randomized to the usual care arm.

#### 1. Potential Benefits to Participating Dialysis Patients

There are no personal benefits to participants. However, all dialysis patients are faced with the metabolic challenges inherent to dialysis treatments and, at one point or another, will face challenges associated with protein loss and protein-energy wasting. The benefit of participating is that this study will attempt to determine whether more aggressive oral nutritional supplementation administration during dialysis improves outcomes; if so, this inexpensive and feasible intervention may be able to be used across dialysis facilities throughout the United States, pending additional advisory opinions by the OIG.

#### 2. Potential Risks to Participating Dialysis Patients

We are not aware of any potential healthcare risks associated with consumption of a small dose of protein supplement. There is a theoretical albeit small risk associated with loss of data confidentiality; however, given that this study is being run by DCI in DCI facilities, data will not be handled differently, aside from periodic dissemination to the DSMB, than it would be in usual clinical and quality improvement activities.

#### 3. Costs to Participating Dialysis Patients

There are no costs for patients to participate in the trial.

#### **3.15 Regulatory Issues**

The NIH-sponsored TiME trial sets a useful important precedent for the conduct of large, pragmatic clinical trials in the dialysis setting, an environment that is unique in healthcare due to the frequent contact between patients and the dialysis facility, the continuous interactions among patients, and

the lack of evidence base to guide treatment decisions. The proposed trial comparing two different nutritional supplement strategies follows the spirit of Sugarman and Califf in their recent viewpoint in JAMA describing the role of pragmatic clinical trials in evidence generation to inform care practices. This study will be requesting a waiver of documentation of consent.

1. *The research involves no more than minimal risk to subjects.*

The most common currently utilized oral nutritional supplement within DCI is Prostat. Pro-Stat is a sugar free liquid protein supplements (medical food), with protein derived from hydrolyzed collagen. In our review at DCI of observational data using a natural experiment to inform a pseudo-randomization cohort design, we found impressive benefits and, critically, no sign of harm associated with Prostat use. Similarly, using similar methodology, Lacson and colleagues found impressive benefits and, critically, no signal of harm with four different protein supplements, including Prostat and ZonePerfect Protein bars. Both Pro-Stat and BodyQuest Protein Ice Cream have very low sodium, potassium and phosphorus content, while ZonePerfect bars selected will be their lowest phosphorus and potassium containing options.

For patients in the intensive supplement group, many will receive more doses of the oral nutritional supplement than they otherwise would have received with usual care. There is no known risk associated with the intake of these supplements. Although there are data in pre-dialysis populations suggesting that high protein intake may be associated with more rapid progression of kidney disease and more uremic symptoms, for patients treated with hemodialysis, this concern is no longer present.

For patients in the usual care group, there is no effect of trial participation on medical care and the risk of loss of confidentiality is minimal. These patients will still be allowed to consume other food items during dialysis as they had previously and will still be administered an oral nutritional supplement if their serum albumin is low.

Regardless of treatment assignment and as they currently do when prescribed the usual care protocol in current clinical practice, patients will have the ability to withdraw from the study, either by stating they do not wish to participate or simply by not taking the oral supplement. This will not in any way affect any other aspect the care delivered to these patients. Lastly, through the MIS, physicians will be aware of treatment assignment and, if desired, have the ability to discontinue the intensive nutritional supplement protocol.

2. *The research involves no procedures for which written consent is normally required outside of the research context.*

Only facilities that are currently utilizing DCI's nutritional supplement protocol will be approached to participate in the study. Therefore, patients will already be familiar with protein supplements either because they took them themselves or saw others taking it in the unit as part of routine care. All data pertaining to treatment and follow-up of study patients, including labs drawn as a part of routine care and outcomes, will be based on the data that is generated in routine practice currently. There will be no paper data collection forms and no additional data collected outside of that routinely and currently collected in clinical practice.

